PROTOCOL NUMBER

405-201-00055

EXECUTIVE SUMMARY

This single-group, open-label study of 50 subjects will explore the potential of centanafadine in promoting smoking abstinence in adult smokers seeking to quit. The efficacy and tolerability of centanafadine at a dose of 400 mg total daily dose (TDD) (200 mg twice daily [BID]) approximately 4 to 6 hours apart (during a 7-week treatment period) will be compared with a benchmark of abstinence based on historical data from clinical trials of varenicline, viewed as the most efficacious pharmacotherapy currently approved by the FDA.

OBJECTIVES AND ENDPOINTS

[figure not shown]
The primary endpoint is the four-week continuous abstinence rate of subjects with the treatment of centanafadine during weeks 4-7. A participant is considered abstinent from combustible cigarettes if he or she self-reports tobacco abstinence (no cigarette smoking, not even a puff) assessed by responses to daily messages throughout the period and has an exhaled carbon monoxide (CO) level of less than 5 ppm using the Vitalograph BreathCO monitor in the office at Visit 5 and Visit 6.

A secondary objective will be to determine if centanafadine yields equivalent efficacy to that of varenicline, with a significant reduction in the incidence of nausea the most prevalent side effect reported following varenicline treatment. Incidence rate of nausea is assessed by self-reported side effects collected via an open-ended question at each study visit.

STUDY DESIGN

This single-group, small-scale, open-label study (N= 50) will evaluate centanafadine SR (400 TDD) as a potential smoking cessation treatment. Participants enrolled in the study will be given centanafadine SR at a dose of 400 mg TDD (200 mg BID) approximately 4 to 6 hours apart for seven weeks.

The study will consist of up to a 28-day screening period, a baseline visit, a 7-week treatment period, and a 7-day safety follow-up period.

DOSING RATIONALE

The 400 mg TDD of centanafadine SR oral tablets (200 mg BID) will be evaluated in this study. This dose was found to produce a significant blockade (>10%) of transporters for serotonin, dopamine, and norepinephrine as well as alleviating symptoms of inattention and hyperactivity/impulsivity in patients with ADHD, without inducing a high incidence of nausea and headache that occur with doses as high as 800 mg.¹

SAMPLE SIZE ESTIMATION

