4.9.4 Daily Message Response Window

The survey response window will be open until the next survey response message is sent.

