The Fagerström Test for Nicotine Dependence is a six-item questionnaire developed by Karl-Olov Fagerström and is used to determine someone’s level of nicotine dependence. The scores obtained on the test allow the classification of nicotine dependence in three different levels: mild (0-3 points), moderate (4-6 points), and severe (7 -10 points).

6.5.16.6 *Smoking History Questionnaire*

The Smoking History is a questionnaire designed to help assess the participant’s current and past smoking habits. This questionnaire will be administered at screening (V1) and will include questions about the number of years participants have smoked combustible cigarettes (CC), the number of CCs per day smoked over the last 12 months, brand of CCs, use of other tobacco products and use of nicotine replacement therapy or other smoking cessation treatments. This questionnaire will also be used to check eligibility criteria.

6.5.16.7 *Other Nicotine Use Questionnaire*

The Other Nicotine Use questionnaire will be used to capture information about the use of nicotine containing products (other than combustible cigarettes). This questionnaire will be given at V2 and all subsequent visits, including safety follow-up.

6.5.16.8 *Minnesota Nicotine Withdrawal Scale (MNWS)*

The MNWS is used to assess nicotine withdrawal symptoms including craving and mood effects. Participants will be asked to assess eight symptoms on a 5-point scale ranging from 0 to 4, where 0 = none, 1 = slight, 2 = mild, 3 = moderate, 4 = severe.

6.5.16.9 *Study Drug Compliance*

Participants will be queried via electronic messages whether they have been compliant with taking the study drug. These messages will commence after the second visit (V2) and continue through the End of Study.

6.5.16.10 *Smoking Status*

Electronic messages will be sent to participants starting after the second visit (V2), through the End of Study, to ascertain the participants smoking status.

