6.7 DAILY MESSAGING

Rose Research Center will utilize eResearch, an IRB approved proprietary mobile electronic application for clinical research studies available in both the iOS and Android app stores. For the purposes of this protocol, the Survey's feature will be utilized to push the daily messages to enrolled participants.

Daily text reminders and/or push notifications may be paired with these daily messages in order to remind participants about the request to complete these assessments.

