6.7.2 Daily Message (Visit 2 through V6)

Participants will receive a push notification with a prompt to a daily survey to assess the following:

- Have you smoked any combustible cigarettes today?
 - If yes, how many cigarettes did you smoke?
- Did you take your 1st dose of study drug today?
- Did you take your 2nd dose of study drug today?
 - If yes, did you take the 2nd dose 4 to 6 hours after the 1st dose?

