11.3.1 Smoking Abstinence

Complete abstinence from combustible cigarette use at each time point will be defined by a self-report of no cigarette smoking (not even a puff) since the prior session, confirmed by an expired air CO reading of less than 5 ppm. The primary outcome will be four-week continuous smoking abstinence during weeks 4-7. An intent-to-treat approach will be taken in which any participants lost to follow-up after receiving the investigational product, or who have smoked during weeks 4-7 will be counted as non-abstinent.

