8.1.1 Primary Efficacy Analyses

The primary endpoint with the treatment of centanafadine is the four-week continuous abstinence rate of subjects during Week 4 to Week 7. A participant is considered abstinent from combustible cigarettes if he or she self-reports tobacco abstinence (no cigarette smoking, not even a puff) assessed by responses to daily messages throughout the period and has an exhaled CO level of less than 5 ppm using the Vitalograph Breath CO monitor in the office at scheduled Week 5 and Week 7. An intent-to-treat approach is

Protocol 405-201-00055 Statistical Analysis Plan

taken in which any participants lost to follow-up / early termination after receiving the IMP, or who have smoked during Week 4 to Week 7 will be counted as non-abstinent.

Primary endpoint calculation:

- Set it as four-week continuous abstinence:
 - If there is no smoking in the self-report.
 - And if subject has exhaled CO level of less than 5 ppm using the Vitalograph BreathCO monitor in the office at scheduled Week 5 or Week 7 value is missing.
 - And if subject has exhaled level of less than 5 ppm using the Vitalograph BreathCO monitor in the office at scheduled Week 7.
 - Missing value check:
 - For CO value, only one missing value is allowed, and Week 7 value cannot be missing.
 - For self-report value, only one missing in each visit Week (7 days) is allowed. The missing value is checked per each week.
- All the others will be set as non-abstinent.
 - Week 7 CO value is missing
 - Two or more missing in self-report in each visit week (7 days)
 - Lost to follow-up/Early termination
 - Subjects with actual data that they were smoking. (CO value \geq 5 ppm or any smoking record in self-report.)

A descriptive statistic will be provided for the continuous smoking abstinence rate during Week 4 to Week 7 with 90% binomial confidence intervals. For all binomial confidence intervals, it is based on normal approximation. If the number of abstinent or the number of non-abstinent ≤ 5 , we will use the exact method.

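### The daily diary item asks only about smoking today, so no listed question covers smoking after the reply or on a tolerated skipped day, and the primary rule can count an isolated lapse as abstinence.

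*Protocol*

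**What the plan says.** **Endpoint.** The Protocol Synopsis (Objectives and Endpoints) counts a participant as abstinent only if no cigarette, not a single puff, was smoked, "assessed by responses to daily messages throughout the period", and CO is below 5 ppm at V5 and V6. SAP 8.1.1 repeats this for Weeks 4 to 7. Protocol 2.1.1 also names daily messages as the source of the self-report.

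**Instrument.** From V2 to V6 the message asks "Have you smoked any combustible cigarettes today", then how many, then two dosing items (Protocol 6.7.2). No send time or earliest reply time is given. Protocol 4.9.4 adds: "The survey response window will be open until the next survey response message is sent". Reminders are optional: "Daily text reminders and/or push notifications may be paired with these daily messages" (Protocol 6.7).

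**Second definition.** Protocol 11.3.1 defines abstinence at each time point by "a self-report of no cigarette smoking (not even a puff) since the prior session", confirmed by CO.

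**Missing diaries.** SAP 8.1.1: "For self-report value, only one missing in each visit Week (7 days) is allowed". Two or more missing replies in a week, a missing Week 7 CO, early termination, loss to follow-up, any CO of 5 ppm or more, or any reported smoking gives non-abstinent. A missing Week 5 CO is tolerated.

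**The concern.** The endpoint is absolute and continuous, but the question is bounded by the calendar day and the moment of reply. A cigarette smoked after the reply lies outside that reply and outside the next day's *today*. A reply given the next morning, which the open window permits, leaves it unclear which day *today* means. A skipped day is not recovered, because the next message does not ask about it. The item also leaves out the single-puff threshold that defines the endpoint.

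Each of these gaps can hide a lapse; none can invent one. In a single-arm study read against a fixed 50% benchmark, no concurrent control arm shares the error, so a hidden lapse goes straight into the rate being compared.

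**Working it through.** **1. Is there another listed question on cigarettes?**

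| Source | Covers cigarettes since the last reply or visit? |
|---|---|
| Daily message (Protocol 6.7.2) | No, today only |
| Other Nicotine Use Questionnaire (6.5.16.7) | No, combustible cigarettes are excluded |
| Telephone contacts, Weeks 2, 4, 6 (6.6.7) | No smoking question specified |
| Visit lists V3 to V6 (6.6.3 to 6.6.6) | No such item named |
| mCEQE at V3 to V6 (6.5.16.2) | Rates the effects of cigarettes; reference period not visible in the text available here; not used in SAP 8.1.1 |
| Protocol 11.3.1 | Presupposes a look-back, with no listed instrument |

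**2. Days that may be unobserved and still count as abstinent**, out of 4 × 7 = 28:
- Primary analysis: 4 × 1 = 4 (14.3%)
- Sensitivity II: 4 × 2 = 8 (28.6%)
- Sensitivity III: 4 × 3 = 12 (42.9%)
- Sensitivity I: no limit

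All three sensitivity analyses relax the diary rule. None probes smoking hidden on an answered day.

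**3. Who slips through?** Let *f* be the chance that a smoking day is hidden from the diary, independently by day. Someone who smokes on *k* days passes the diary with probability *f*^*k*. The documents give no *f*. Assuming 16 waking hours and a reply 1 to 8 hours before sleep, the after-reply gap alone gives *f* from 1/16 (6%) to 8/16 (50%).

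| *f* | *k* = 1 | *k* = 2 | *k* = 3 |
|---|---|---|---|
| 0.25 | 25% | 6.3% | 1.6% |
| 0.50 | 50% | 25% | 12.5% |

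Repeated smoking is usually caught; a single lapse often is not. These figures ignore CO, which lowers them.

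**4. What could it do to the conclusion?** This point disputes none of the plan's own figures. The exact 90% limits in SAP Table 4-1 reproduce to five decimals (at 0.5: 0.37625 to 0.62375). The decision thresholds are redacted in Protocol 11.1, so a cut-off has to be inferred:
- 31/50 is the smallest count whose normal-approximation 90% lower limit exceeds 50%: 0.62 − 1.645 × √(0.62 × 0.38/50) = 0.507. For 30/50 the limit is 0.486.
- A search over rules of the form *at least r1 abstinent, or at least r0 abstinent with at most c nausea cases*, taking the two outcomes as independent, fits best at (31, 20, 9). It gives power of 73.7%, 75.7% and 94.3% against the stated 74%, 76% and 94%, but a type I error of 9.49% against 9.87%. The fit is close, not exact.

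Let *m* be the share of true non-abstainers counted as abstinent. At a true rate of 50% the observed rate is 0.5 + 0.5*m*. The binomial probability of reaching the cut-off with n = 50 is:

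| *m* | Observed rate | ≥ 30 | ≥ 31 | ≥ 32 |
|---|---|---|---|---|
| 0 | 50% | 10.1% | 5.9% | 3.2% |
| 2% | 51% | 12.9% | 7.8% | 4.4% |
| 5% | 52.5% | 17.9% | 11.4% | 6.8% |
| 10% | 55% | 28.6% | 19.7% | 12.7% |

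Both *m* and the cut-off are assumptions.

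**The case against.** - **A look-back is defined.** Protocol 11.3.1 asks for self-report since the prior session, so a reader who concludes that such smoking is never asked about goes beyond the text. This stands. What the documents support is that the definition has no listed instrument, conflicts with the daily-message basis and plays no part in the SAP algorithm.
- **Other rules limit the gap.** CO at Weeks 5 and 7 and the failure rule for two missing replies in a week catch much smoking. This stands, but neither catches an evening lapse on an answered day away from a CO visit.
- **The open window helps.** It allows bedtime replies and reduces skipped days, and the item on the second dose discourages morning replies. This is fair: the window does not cause the after-reply gap. Its drawback is the ambiguous *today*. With the second dose due 4 to 6 hours after a morning dose, an afternoon reply remains possible.
- **The net bias is unknown.** It is tempting to infer that the reported rate is overstated. Other rules push it down: missing replies count as failure, and messages stop at V6 under 6.7.2 although V6 may fall three days before SAP Week 7 ends on Day 49 (Protocol 6.5.16.10 instead continues them to End of Study). The documents also do not say how the varenicline trials ascertained smoking. This stands.
- **The illustration is not derived from *f*.** This is correct. At *f* = 1/16 the after-reply gap alone cannot push *m* above 6.25%, even if every non-abstainer lapsed exactly once; 10% would also need lapses on skipped days, and those lapsers must still pass CO. Nor does the SAP plan a test: it reports a rate with a 90% interval. The table therefore shows sensitivity, not the trial's error rate.

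**Conclusion.** The measurement gap is real on the page. Followed as written, the plan can class an isolated lapse as four-week continuous abstinence, although its own definition is meant to count that lapse as failure. This mechanism acts in one direction only, upward. The text does not establish that the final rate will be too high overall, or by how much: that depends on reply times, the share of non-abstainers with only one or two lapses, and how many of them pass CO, none of which is given. The one size that follows directly from the documents is the 4 of 28 days that may go unreported. The rise from 5.9% to between 11.4% and 19.7% rests on an assumed 5% to 10% misclassification, a true rate of 50% and an inferred cut-off of 31/50. The change is worth making because it is nearly free and bears on the primary endpoint.

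**What to change.** 1. **Protocol 6.7.2:** reword the item to *Since your last daily report, have you smoked any cigarette, even a puff? If yes, on which day(s) and how many?* This covers the hours after each reply and any skipped day, and removes the ambiguity of a late reply.
2. **V5 and V6:** add a dated cigarette look-back asking on which dates since the last visit any cigarette was smoked. Dates are essential: V4 may fall at about Day 18 (21 − 3), so an undated yes at V5 could refer to smoking before Week 4. A look-back at V4 would mostly cover time outside the endpoint and is not needed for it.
3. **SAP 8.1.1:** add that any reported smoking dated within Days 22 to 49 (Weeks 4 to 7 in Table 5.4-1), from either source, means non-abstinent.
4. **Definitions:** reconcile the Synopsis, Protocol 2.1.1, Protocol 11.3.1 and SAP 8.1.1 so that one self-report definition applies and each source it names is actually collected.

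The cost is one reworded survey item, one visit question and one SAP line, with no extra visits. The observed rate may be slightly lower.

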6.8 SCHEDULE OF EVENTS

Study Week	SCR	Wk 0 Baseline		Wk 1 (+ 3 days)	Wk 2 - Wk 3 (± 3 days)	Wk 4 - Wk 5 (± 3 days)	Wk 6 - Wk 7 (± 3 days)	Wk 8 (+ 2 days)
Visit	V1	V2		V3	V4	V5	V6	Safety Follow-up
IMP Timeline		Day -1	Day 1 IMP	Wk 1 IMP	Wk 3 IMP	Wk 5 IMP	Wk 7 IMP	
Informed Consent	x							
Inclusion/Exclusion Criteria	x	x						
Enrollment		x						
Visit Preparation	x	x		x	x	x	x	
Visit Reminder Calls	x	x		x	x	x	x	
Telephone Contact -(Day 1, Wk 2, Wk 4, Wk 6, and 7 day F/U)			x		x	x	x	x
Questionnaires								
Reasons to Smoke		x						
Smoking History	x							
Other Nicotine Use		x		x	x	x	x	x
Registration Form	x							
Medical History with Review of Systems	x							
Modified Cigarette Evaluation Questionnaire Extended (mCEQE)		x		x	x	x	x	x
The Fagerström Test for Nicotine Dependence (FTND)		x						x
Modified Shiffman-Jarvik Withdrawal Scale		x		x	x	x	x	
Minnesota Withdrawal Questionnaire		x		x	x	x	x	x
The Columbia-Suicide Severity Rating Scale (C-SSRS)	x	x		x	x	x	x	
Smoking Status (via daily messages)	x	x	x	x	x	x	x	
Medication Adherence (via daily messages)		x	x	x	x	x	x	
Blood Samples								
Clinical Chemistry	x				x		x	
CBC w/Diff & Platelet Count	x				x		x	
Serum Pregnancy Test*	x							
HbA1c	x							
PK Blood Draws					x		x	
CCI								
Urine Samples								
Urinalysis Safety Panel	x						x	
Drug Screen	x				x	x		
Pregnancy		x		x	x	x	x	
Other Assessments								
Prior and Concomitant Medication Assessment and Medical Review	x	x		x	x	x	x	x
Concomitant Disease Assessment and Medical Review	x	x		x	x	x	x	
CO Breath Test	x	x		x	x	x	x	
ECG	x						x	
Blood Pressure - Sitting and Standing Positions	x	x		x	x	x	x	
Heart rate	x	x		x	x	x	x	
Temperature	x	x		x	x	x	x	
Respiratory rate	x	x		x	x	x	x	
Weight	x	x		x	x	x	x	
Physical Examination (as needed)	x	x		x	x	x	x	
Alcohol Breath Test	x							
Procedures								
AE Interview and Assessment		x		x	x	x	x	x
Collect Used/Unused IP				x	x	x	x	
Dispense IP		x		x	x	x		
IMP Dosing			x	x	x	x	x	

* Serum pregnancy test will be done if urine pregnancy test is positive

Table 6 - Schedule of Event

7 RISK / BENEFIT INFORMATION

7.1 POTENTIAL BENEFITS

The participants will be encouraged to quit smoking, which would significantly reduce their risk of smoking-related diseases.

7.2 IMPORTANCE OF KNOWLEDGE TO BE GAINED

The proposed study could lead to the development of a new approach to smoking cessation that would have a major positive impact on public health worldwide along with associated comorbid conditions.

7.3 POTENTIAL RISKS

7.3.1 Centanafadine SR

The most common adverse effects reported in other studies of centanafidine SR include: decreased appetite, headache, nausea, dry mouth diarrhea, fatigue, insomnia, rash (refer to [Section 9.5](#) for additional information), dizziness, heart rate increase when standing from a sitting position, irritability, abdominal pain, change in sense of taste.¹

7.3.2 Tobacco Withdrawal

To the extent that nicotine or other tobacco smoke constituent intake is reduced or eliminated, participants may experience tobacco withdrawal symptoms, including craving, difficulty concentrating, mood disturbance and increased appetite/weight gain.

7.3.3 Blood Draw

The risks associated with venipuncture are minimal and include momentary discomfort and/or bruising. Infection, excess bleeding, clotting, and fainting are also possible, although unlikely.

7.4 CONCOMITANT MEDICATIONS

All medication taken 30 days prior to the screening visit (V1) and during the study will be documented using a source document. Medications which are stopped before V2 will be considered as prior medication. Medication which was started prior to V1 and which is still being taken by the subject during the study as well as medication that is initiated after V2 will be considered as a concomitant medication. This applies to both prescription and over-the-counter products (e.g., vitamins).

Records of prior and concomitant medications taken include the drug name (preferably both generic and trade name), route of administration, dose/unit, frequency of use, indication, the start and if applicable, the stop date. Any therapy changes (including changes of regimen) during the study have to be documented.

7.5 PROTECTION AGAINST RISKS

Participants will be screened medically and monitored throughout the study. Study participants will receive detailed instructions on the use of the IMP distributed to them, in order to minimize the possibility of misuse. Participants will be instructed to keep the study drug away from children and pets.

Participants will be instructed to report any side effects to study staff, who will communicate these reports to the medical staff. The most appropriate course of action will be determined, which may include options for termination of exposure to the study drug. Participants will, however, be reminded that they have the option to withdraw from the study at any time. Participants will also be given a 24-hour emergency contact number in the event that side effects or adverse events occur between sessions.

7.5.1 Blood Pressure Monitoring

Cigarette smoking affects blood pressure in many ways, including stimulation of the sympathetic nervous system, but also through acute inflammation, impairment of endothelial function, and increased arterial stiffness.²⁶ In 2017, the American College of Cardiology set forth stricter recommendations for treatment of elevated blood pressure, with the goal of commencing treatment (lifestyle changes and/or medication) starting at 130/80, vice 140/90.²⁷ The definition of systemic arterial hypertension (commonly known as hypertension) did not change with these new recommendations from the American College of Cardiology. Hypertension is characterized by persistently high blood pressure in the systemic arteries, with an “Office BP” of \geq 140 mmHg systolic and \geq 90 mmHg diastolic.²⁸

This study will use a blood pressure of 150/95 as a cutoff for eligibility, recognizing that most participants have recently smoked just prior to arriving for the screening process, and that many of them will have additional sympathetic activation through the ingestion of caffeinated beverages.

Any participant who presents with blood pressure $>$ 140 mmHg systolic and/or $>$ 90 mmHg diastolic will be counselled, with recommendations to monitor blood pressure at home and follow up with their primary care provider. Participants who enroll in the study will have blood pressure checks at every office visit.

8 QUALITY CONTROL AND QUALITY ASSURANCE

8.1 MONITORING ACTIVITIES

An independent Monitor will be contracted by RRC and will be responsible for the monitoring activities. Monitoring will be performed as per the agreed monitoring plan. A minimum of the following types of monitoring visits will occur for this study.

8.1.1 Site Initiation Visit (SIV)

A Site Initiation Visit will be conducted by the Monitor prior to site activation to confirm preparedness for protocol execution, satisfactory site facilities, clarify the applicable regulations and requirements of the protocol, carefully review the process of implementing the protocol at the site and conduct any necessary training prior to activating the site for enrollment.

